In adult studies of carcinomatosis, there were no procedure related mortalities; morbidity included renal impairment, ascites, and pancreatitis. Dose limiting toxicity included grade III leukopenia, grade IV neutropenia and grade III and IV thrombocytopenia at the higher doses only (greater than 800 mg/M). (20, 21) Specifically, no patient had a prolonged postoperative ileus and no adverse effect on wound healing was observed. Following surgery, the median time before tolerating enteral feeds was 5 days (range 1-7 days), and patients could tolerate a regular diet at a median of 7 days (range 4-8 days). Neither patient who had undergone bowel resection and anastomosis followed by HIPEC had any anastomotic complication. One patient suffered a subfascial hematoma incurred from trauma to the left inferior epigastric artery. (20) In the mesothelioma study, the MTD of cisplatin was 300 mg/M. Above this dose there were significant rises in creatinine and one patient required temporary hemodialysis. (21) There have not been any untoward effects of the HIPEC on the ability of these patients to heal incisional wounds and convalesce uneventfully.

This intraoperative treatment using HIPEC in children has provided some very encouraging results. The phase I study of HIPEC in children done here (protocol #2005-0917) proved to be safe. There were no protocol related deaths. Two SAE's included temporary cardiomyopathy likely related to the 4 kg+ tumor resected and supraventricular tachycardia likely related to central venous catheter malposition. Several children had temporary increased creatinine, up to 1.9. However, no problems were seen with urinary output; serum creatinine returned to normal within 1-2 weeks without treatment or dialysis.

Preliminary results suggest 3 year disease free survival is 71% (compared to 26% in historic controls) and disease free interval is increased 5 times from 1.6 to 9 months in the subset of patients with DSRCT. The 2 sarcoma patients died within 6 months and one mesothelioma patient is alive with minimal disease. Another mesothelioma patient in 3rd relapse was treated with surgery + HIPEC is >2 years from surgery. In summary there appears to be benefit in many and we have reached a dose limiting toxicity (DLT), elevated creatinine using HIPEC with cisplatin at 150 mg/M.

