### 1.0 Primary objectives of the study

**Primary objective 1:** To determine the efficacy of HIPEC using hyperthermic cisplatin given as a continuous perfusion after complete abdominal tumor excision in patients with DSRCT.

**Primary objective 2:** To determine the morbidity of extensive tumor resection and HIPEC on patients with DSRCT and other non-carcinoma tumors with extensive abdominal disease.

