4.2.3 In addition, toxicity will be monitored closely in all patients. The evaluation of the toxicity data will begin after enrollment of 8 patients. Denote the probability of toxicity by  $\theta_E$ , where toxicity is defined as any Grade 3 or greater renal, cardiac, respiratory or Grade 4 hematologic complications attributable to HIPEC. We assume  $\theta_E \sim \text{beta}(0.6, 1.4)$ . Our stopping rule is given by the following probability statement:  $\Pr(\theta_E > 0.30 \mid \text{data}) > 0.8$ . That is,

we will stop the trial if, at any time during the study, we determine that there is more than 80% chance that the toxicity rate is more than 30%. Stopping boundaries corresponding to this stopping rule are to terminate the trial if (# Grade 3 or greater renal, cardiac, respiratory or Grade 4 hematologic complications) / (# patients evaluated)  $\geq 4/8, 5/9, 6/12, 7/15, 8/18$ . That is, the trial will be stopped if 4 or more patients out of 8 patients, 5 or more patients out of 9 patients, and 6 or more patients out of 10, 11 and 12 patients, 7 or more patients out of 13, 14 and 15 patients, 8 or more patients out of 16, 17, 18 patients experience toxicity. Please note that for the first 8 patients, if 4 or more out of 4-7 patients experience toxicity, the trial will also be stopped, because the stopping boundary is already passed. The operating characteristics are summarized in [Table 2](#).

4.2.4 Analysis Plan: For discrete or categorical data, descriptive statistics will include tabulations of frequencies. For continuous data, summary statistics including n, mean, standard deviation, median, minimum and maximum will be computed. The median time to progression and its 95% confidence interval will be estimated. Kaplan-Meier method, Log rank test and Cox proportional hazards regression modeling will be utilized to analyze time to progression and overall survival. The study will use Department of Biostatistics Clinical Trial Conduct website to conduct/monitor with regard to the defined Bayesian rules.

Table 1. Operating characteristics for the design

True median Time to progression (month)	Pr(stop early)	Average Number of Patients Treated (25th, 75th percentiles)
1	0.998	4 (1,5)
1.6	0.775	9 (2,18)
3.2	0.178	17 (2,20)
4	0.126	18 (20,20)

Table 2.

True toxicity rate	Early Stopping Probability
0.1	0.006
0.2	0.094
0.3	0.344
0.4	0.665
0.5	0.897

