5.2.2 Risks and Benefits- The potential benefit to a patient undergoing this therapy would be palliation in terms of preventing or delaying intra-abdominal tumor progression, which can be a devastating and painful source of symptoms and cause for demise. In addition, significant tumor response may extend survival. The risks of this protocol include those inherent to extensive abdominal surgery. This includes postoperative bleeding, wound infection, intra-abdominal abscess, wound dehiscence, enterocutaneous fistula, anesthetic complications and postoperative death. Also, toxicities of cisplatin therapy place the patient at risk. In addition, in the case of intra-abdominal catastrophe, patients may require re-operation.

5.2.3 Alternatives - Children dying of extensive peritoneal, retroperitoneal disease, or carcinomatosis, suffer with recurrent bowel obstructions, nausea, vomiting, abdominal pain, inability to pass stool, poor appetite and in late stages refractory ascites. Because there is presently no other treatment alternatives offered in this clinical scenario, aggressive treatment as a means of palliation and survival benefit, are justified. There have been many phase I and II trials in adults in which long term remissions after HIPEC in patients who were otherwise terminal, have been realized. Patients will be informed of other experimental chemotherapy options available.

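### The toxicity stopping rule omits Grade 5 hematologic events and does not count procedure-related death in itself; such a death enters only through a listed toxicity attributed to HIPEC.

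*Combined protocol and SAP*

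**What the plan says.** Section 4.2.3 defines the event behind the toxicity parameter as "any Grade 3 or greater renal, cardiac, respiratory or Grade 4 hematologic complications attributable to HIPEC". The numerator of the stopping boundary repeats the same organ and grade list: "Grade 3 or greater renal, cardiac, respiratory or Grade 4 hematologic complications". In both places the words for higher grades are attached to the renal, cardiac and respiratory classes and not to the hematologic class. Death is not named.

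The trial stops when there is "more than 80% chance that the toxicity rate is more than 30" per cent, under a beta(0.6, 1.4) prior. On timing: "The evaluation of the toxicity data will begin after enrollment of 8 patients". The printed boundaries are "4/8, 5/9, 6/12, 7/15, 8/18".

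Three other places bear on the point:
- Primary objective 2 (section 1.0) is "To determine the morbidity of extensive tumor resection and HIPEC on patients with DSRCT" and other non-carcinoma tumors, so it covers the whole operation.
- Section 5.2.2 lists the risks of extensive abdominal surgery, including bleeding, abscess and fistula, and ends the list with "anesthetic complications and postoperative death".
- Section 4.9 requires serious adverse events to be captured from consent to 30 days after the last dose and reported to the IRB. It sets no stop or pause for deaths.

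**The concern.** This is the only formal safety stop in a trial open from age 1 (section 2.1.1), and section 4.2.1 names only toxicity and futility as grounds for stopping. Three features of the event definition narrow what it can register.

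1. A fatal hematologic event is, on the wording, less countable than a Grade 4 one.
2. A procedure-related death whose cause is outside the listed classes does not count as such.
3. Only events attributed to HIPEC count, yet resection and perfusion are given in one operation, so attribution decides what the rule sees. The phase I experience in the Background shows how this can go. One of the two serious adverse events was "temporary cardiomyopathy likely related to the 4 kg+ tumor resected"; the other, a supraventricular tachycardia, was put down to catheter position. Both are cardiac, a listed class, but with the same attribution neither would count here, whatever its grade.

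The futility rule does not close the gap. Section 4.2.1 ends follow-up at death but does not say whether death is an event or a censoring for time to relapse. At stake is whether the monitoring would respond if procedure-related deaths occurred.

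**Working it through.** **Step 1. Which events the definition counts (literal reading of 4.2.3).**

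| Event | Counted? |
|---|---|
| Grade 3, 4 or 5 renal, cardiac or respiratory, attributed to HIPEC | Yes |
| Grade 4 hematologic, attributed to HIPEC | Yes |
| Grade 5 hematologic | No |
| Death from bleeding, sepsis or leak, with a listed toxicity attributed to HIPEC in the same patient | Yes, through that toxicity |
| The same death without such a toxicity | No |
| Listed organ event attributed to the resection | No |

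**Step 2. Reproduce the plan's own figures.** Inputs from 4.2.3: prior beta(0.6, 1.4), limit 0.30, cut-off 0.80, first look at 8 patients. After x events in n patients the posterior is beta(0.6 + x, 1.4 + n − x). The boundary is the smallest x for which the posterior probability of a rate above 0.30 exceeds 0.80. The stop probability follows from an exact patient-by-patient binomial recursion.

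The rule gives 4 events at n = 8; 5 at 9 to 11; 6 at 12 to 14; 7 at 15 to 17; 8 at 18 to 20; 9 at 21 to 22.

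| True rate | Table 2 | Posterior rule, looks at 8–19 | Posterior rule, looks at 8–22 | Printed boundaries, to 18 |
|---|---|---|---|---|
| 0.1 | 0.006 | 0.007 | 0.007 | 0.005 |
| 0.2 | 0.094 | 0.094 | 0.098 | 0.068 |
| 0.3 | 0.344 | 0.345 | 0.370 | 0.266 |
| 0.4 | 0.665 | 0.669 | 0.710 | 0.570 |
| 0.5 | 0.897 | 0.895 | 0.923 | 0.834 |

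The posterior rule with looks to 19 patients reproduces Table 2. The printed boundaries differ from the posterior rule; that is a separate issue, so results are given under both.

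**Step 3. Illustrate the effect of uncounted deaths.** The documents give no rate, so d below is an assumption. Let t be the counted toxicity rate and d the rate of procedure-related deaths from causes outside the list, independent of counted toxicity. As written, the rule sees t whatever d is. If deaths count, it sees 1 − (1 − t)(1 − d). For t = 0.20 and d = 0.10 this is 1 − 0.80 × 0.90 = 0.28. A patient with both counts once, so the deaths add 8 points, not 10.

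| t | d | Rate if deaths count | Posterior rule, 8–22: as written → counted | Printed boundaries, to 18: as written → counted |
|---|---|---|---|---|
| 0.10 | 0.05 | 0.145 | 0.007 → 0.029 | 0.005 → 0.021 |
| 0.10 | 0.10 | 0.190 | 0.007 → 0.081 | 0.005 → 0.057 |
| 0.20 | 0.05 | 0.240 | 0.098 → 0.186 | 0.068 → 0.129 |
| 0.20 | 0.10 | 0.280 | 0.098 → 0.303 | 0.068 → 0.214 |
| 0.30 | 0.10 | 0.370 | 0.370 → 0.615 | 0.266 → 0.476 |

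Under the version that matches Table 2 (looks to 19), the case t = 0.20, d = 0.10 moves from 0.094 to 0.283.

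**Step 4. What counting deaths does not achieve.** With t = 0 and d = 0.10 the widened rule sees a rate of 0.10 and stops with probability 0.007 (0.005 under the printed boundaries).

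**The case against.** A reader might infer that deaths from bleeding, sepsis or leak could never trigger the rule, or that it misses most treatment-related deaths. Neither follows. Fatal renal, cardiac and respiratory events attributed to HIPEC already count. A patient who dies of sepsis or bleeding counts if a listed toxicity attributed to HIPEC also occurred; the death does not cancel it. The documents give no distribution of causes of death, so no claim about most deaths can be supported. The Background reports no protocol-related deaths in phase I and no procedure-related mortality in the adult studies.

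The Grade 5 omission is probably a drafting slip, and in practice few would exclude a patient who passed through Grade 4 before dying. That is fair, but the wording appears twice and is easily corrected.

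A stopping rule need not use the same events as a descriptive objective. Wider morbidity is captured: adverse events are assessed to 6 months (4.5.3), Grade 3 to 5 events are recorded whatever the attribution (4.9), and 4.2.4 provides tabulations. Limiting the rule to HIPEC also targets the investigational component, whose phase I dose-limiting toxicity was raised creatinine. This stands as a reason to leave the choice of other surgical complications to the sponsor. It does not explain why procedure-related death has no place in any stopping rule, since recording and IRB reporting do not stop the trial.

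Finally, the 30% limit and the prior (mean 0.6/2.0 = 0.30) were set for the narrower event. That stands and is carried into the fix.

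**Conclusion.** The point holds in a limited form. On the wording of 4.2.3, Grade 5 hematologic events are omitted, and a procedure-related death without a listed toxicity attributed to HIPEC adds nothing to the only formal safety stop. Nothing elsewhere in the documents closes that gap. The stronger readings described under the objection are not supported.

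This conclusion rests on the text and needs no calculation. The size does rest on assumption. At 20% counted toxicity and an assumed 10% of independent, otherwise uncounted deaths, the stop probability goes from 0.098 to 0.303 (posterior rule) or from 0.068 to 0.214 (printed boundaries). At lower rates the change is smaller in absolute terms. The direction is the same under every version of the boundaries tried. Adding deaths to a composite judged against 30% makes the rule more complete but does not turn it into a mortality limit.

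**What to change.** - In both places in 4.2.3, change the hematologic component to Grade 4 or greater.
- Count as a toxicity event any death within the 30-day serious adverse event window of section 4.9 that is not clearly unrelated to the procedure.
- Reconcile the restriction to events attributable to HIPEC with primary objective 2. The sponsor decides which other surgical complications, if any, should count.
- Confirm that the 30% limit and the beta(0.6, 1.4) prior still suit the slightly wider event.

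The posterior rule and its operating characteristics by true rate do not change, because they depend only on the event rate; what changes is which patients contribute to that rate.

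Cost: a short wording change and the sponsor's confirmation, with no new data collection. The downside is a somewhat higher chance of stopping when procedure-related deaths occur.

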## 4.2 Response Criteria and Statistical Considerations

4.2.1 This is a phase II study of continuous hyperthermia peritoneal perfusion (HIPEC) in patients with desmoplastic round cell tumor (DSRCT) and non-DSRCT patients. The primary objective is to assess the efficacy of this treatment, with a primary endpoint of time to relapse. The historical median time to relapse for DSRCT patients without HIPEC treatment was about 1.6 months. A maximum of 22 patients will be enrolled in MDACC at an estimated accrual rate of 1 patient every 2 months including a total of 5 non-DSRCT patients. Patients will be followed up until relapse, death or for 6 months after the treatment, whichever ever occur first. It would be encouraging if the median time to relapse could increase to 3.2 months with the HIPEC treatment. The toxicity and efficacy will be monitored during the study, and all the data will be used to update the prior distributions for toxicity and efficacy parameters. The study will be stopped for toxicity and futility based on the following stopping rules.

4.2.2 The primary endpoint TTP will be monitored using the method of Thall et al. (23). Denote median (TTP) =  $m_H$  for patients without HIPEC treatment and  $m_E$  for patients with HIPEC treatment. We assume that TTP is distributed exponentially with mean of  $m_H$  and  $m_E$ , respectively, in patients without and with HIPEC treatment. Under a Bayesian model, we will further assume that  $m_H$  has an inverse gamma (IG) prior with parameters (16.2, 24.3), with a mean of median TTP=1.6 months and variance = 0.18. We also assume that  $m_E$  follows IG prior (2.03, 1.64) with the same median TTP as  $m_H$  but with a much larger variance (100) to reflect much greater uncertainty about TTP in patients with HIPEC treatment. The TTP data will be monitored continuously, and the study will be terminated early if  $\Pr(m_H + d < m_E \mid \text{data}) < 0.05$ , where  $d = 1.6$  month. Specifically, the trial will be stopped early if, given the current data, there is less than 5% chance that the median TTP will improve by more than 1.6 month in patients treated with HIPEC, compared to those without HIPEC treatment. The operating characteristics of this decision rule are summarized in [Table 1](#).

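### The printed toxicity stopping counts require one event more than the stated Bayesian rule at n = 10, 11, 13, 14, 16 and 17, and they do not reproduce Table 2

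*Combined protocol and SAP*

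**What the plan says.** Section 4.2.3 defines toxicity, gives it a beta(0.6, 1.4) prior and starts evaluation after 8 patients. The rule is a probability statement, Pr(θ_E > 0.30 | data) > 0.8. The section restates it in words: "we will stop the trial if, at any time during the study", it is found that "there is more than 80% chance that the toxicity rate is more than 30" per cent.

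Integer counts follow, introduced by "Stopping boundaries corresponding to this stopping rule are to terminate the trial if". A short form lists 4/8, 5/9, 6/12, 7/15 and 8/18. A sentence then spells these out: 4 of 8, 5 of 9, "6 or more patients out of 10, 11 and 12 patients, 7 or more patients out of 13, 14 and 15 patients", and "8 or more patients out of 16, 17, 18 patients experience toxicity". Nothing is listed after 18. A further note stops the trial if 4 or more of the first 4 to 7 patients have toxicity.

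Table 2 gives early stopping probabilities of 0.006, 0.094, 0.344, 0.665 and 0.897 at true toxicity rates of 0.1 to 0.5, without stating a sample size. Section 4.2.1 says "A maximum of 22 patients will be enrolled in MDACC". Section 4.2.4 says "The study will use Department of Biostatistics Clinical Trial Conduct website to conduct/monitor with regard to the defined Bayesian rules".

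**The concern.** The counts are offered as equivalent to the probability rule, but the short form and the spelled-out sentence appear to run in opposite directions. With this prior, 5/9, 6/12, 7/15 and 8/18 are each the first sample size at which that count becomes the boundary, so each count should carry forward until the next one starts. The sentence carries 6, 7 and 8 backwards instead.

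If so, the protocol gives two different safety instructions at several sample sizes, and the printed one is always the more lenient. Anyone working from the printed counts would keep enrolling after the protocol's own safety criterion had been met. A reader who relies on Table 2 to judge the monitoring would be looking at the properties of a different boundary.

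**Working it through.** **Inputs (all from 4.2.1 and 4.2.3).** Prior beta(0.6, 1.4); threshold 0.30; cut-off 0.8; first look at n = 8; the printed counts; Table 2; maximum enrolment 22.

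**Step 1: boundary from the stated rule.** After x toxicities in n patients, θ_E follows beta(0.6 + x, 1.4 + n − x). The boundary is the smallest x for which the tail above 0.30 exceeds 0.80. For example, 5/10 gives beta(5.6, 6.4), with a tail of 0.880, so the trial stops. 4/10 gives 0.711, so it continues.

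| n | Rule stops at | Printed count | Pr(θ_E > 0.30) at the rule's count | at one event fewer |
|---|---|---|---|---|
| 8 | 4 | 4 | 0.846 | 0.631 |
| 9 | 5 | 5 | 0.922 | 0.782 |
| **10** | **5** | **6** | 0.880 | 0.711 |
| **11** | **5** | **6** | 0.829 | 0.638 |
| 12 | 6 | 6 | 0.905 | 0.772 |
| **13** | **6** | **7** | 0.865 | 0.709 |
| **14** | **6** | **7** | 0.818 | 0.644 |
| 15 | 7 | 7 | 0.893 | 0.766 |
| **16** | **7** | **8** | 0.855 | 0.710 |
| **17** | **7** | **8** | 0.811 | 0.651 |
| 18 | 8 | 8 | 0.883 | 0.763 |
| 19 | 8 | none | 0.847 | 0.712 |
| 20 | 8 | none | 0.807 | 0.658 |
| 21 | 9 | none | 0.876 | 0.762 |

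The short-form entries all agree with the rule. The spelled-out counts differ at six of eleven sample sizes, each time by exactly one event.

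**Step 2: reproduce Table 2.** Stopping probabilities come from an exact binomial recursion with a look after every patient. Each outcome is assumed known before the next patient enters.

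| Boundary used | 0.1 | 0.2 | 0.3 | 0.4 | 0.5 |
|---|---|---|---|---|---|
| Table 2 as printed | 0.006 | 0.094 | 0.344 | 0.665 | 0.897 |
| Stated rule, looks at 8–19 | 0.007 | 0.094 | 0.345 | 0.669 | 0.895 |
| Printed list alone, nothing after 18 | 0.005 | 0.068 | 0.266 | 0.570 | 0.834 |
| Printed list to 18, stated rule at 19–21 | 0.005 | 0.077 | 0.317 | 0.657 | 0.897 |
| Stated rule, looks at 8–21 (maximum 22) | 0.007 | 0.097 | 0.362 | 0.697 | 0.913 |

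The stated rule with looks at 8 to 19 is within 0.004 of every Table 2 entry. That pattern implies a maximum of 20, with the last patient not counted as an early stop. The maximum of 20 is an inference, but Table 1's quartiles of 20 and 20 point the same way. Neither version of the list reproduces the table. The note on 4 events in the first 4 to 7 patients leaves the stopping probabilities unchanged.

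**Step 3: effect of the lenient counts alone.** Compare the last two rows, which treat n = 19 to 21 identically.
- At a true rate of 0.4: 0.697 − 0.657 = 0.040 less stopping. The average number treated is 14.3 against 13.4, a difference of 0.9 (maximum 22, including the note on 4 to 7 patients).
- At a true rate of 0.3: 0.362 − 0.317 = 0.045 less stopping.
- With looks only to n = 19, the loss at 0.4 is 0.669 − 0.611 = 0.058.

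**Step 4: how often the conflict arises.** The probability that a trial first meets the rule at one of the six disputed counts is 0.002, 0.036, 0.141, 0.246 and 0.244 at true rates of 0.1 to 0.5.

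**The case against.** The strongest reply is that the protocol does indicate what governs. Section 4.2.3 introduces the probability statement as the stopping rule itself, and the counts come in only as its consequence. Section 4.2.4 has a website monitor the Bayesian rules. If that website computes the posterior, the trial is run as intended and the error lies only in the printed text. This carries weight: the wording does lean towards the posterior. But the same section also says, without qualification, that the trial will be stopped at the listed counts, and no sentence says which prevails when they differ.

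A second reply is that the effect is modest, and this is partly right. The 9.5-point gap to Table 2 at a true 40% rate (0.665 − 0.570) assumes no monitoring after 18, which contradicts the rule's application throughout the study. With the rule applied at 19 to 21, the gap to Table 2 is 0.8 points at 40%, zero at 50%, and at most 2.7 points (at 30%). The roughly 25% chance of reaching a disputed count at a true 40% rate is also not a chance of wrongly completing enrolment, because most of those trials stop at a later look. The like-for-like cost is the 4 points and 0.9 patients above.

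Third, leaving out a look at n = 22 is a convention, chosen because such a look cannot stop accrual. Including it gives 0.007, 0.098, 0.370, 0.710 and 0.923, which is further from Table 2.

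**Conclusion.** The concern holds. The printed counts do not follow from the rule they are said to represent. They are one event too lenient at six of eleven sample sizes, and none of the six is a rounding case (the closest posterior is 0.811 against 0.80). Table 2 describes neither the printed list nor, as far as can be inferred, a trial of up to 22. Sample sizes 19 to 21 have a rule but no printed count.

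The average cost if the list is followed is modest: about 4 points less stopping and 0.9 more patients at a true 40% rate. It should still be corrected before the boundary is used, because this is the formal toxicity stopping rule and it must have one meaning. The posterior values need only the stated prior and threshold. The operating characteristics also assume a look after each patient with prompt outcomes.

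**What to change.** Reconcile the probability rule, the integer list, Table 2 and the maximum sample size. Add a line saying which governs and what the monitoring website applies.

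- If the stated rule and prior are kept, the list they generate is ≥4 at n = 8, ≥5 at 9–11, ≥6 at 12–14, ≥7 at 15–17, ≥8 at 18–20 and ≥9 at 21. Table 2 for a maximum of 22, with looks at 8 to 21, becomes 0.007, 0.097, 0.362, 0.697 and 0.913. State whether a look at n = 22 counts.
- If the printed list is what was intended, restate the rule so that it yields those counts, extend the list beyond 18, and recompute Table 2 from it.

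The cost is one sentence, one table and one governing line, with no extra patients. Keeping the stated rule means somewhat earlier stopping than under the list. At a true 30% rate, for example, 36% of trials would stop rather than 32% (list to 18, then the rule).

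### The printed toxicity boundaries in 4.2.3 are one event too high at six sample sizes and end at 18 of 22 patients, so they do not deliver Table 2

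*Combined protocol and SAP*

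**What the plan says.** Section 4.2.1 sets the size: "A maximum of 22 patients will be enrolled in MDACC", of whom 5 are non-DSRCT. Section 4.2.3 says that "toxicity will be monitored closely in all patients" and that "The evaluation of the toxicity data will begin after enrollment of 8 patients". With a beta(0.6, 1.4) prior for the toxicity rate theta_E, the rule is Pr(theta_E > 0.30 | data) > 0.8, and its scope is the whole trial: "we will stop the trial if, at any time during the study" this probability is exceeded.

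The boundaries are then given twice. As fractions they are "4/8, 5/9, 6/12, 7/15, 8/18". In prose they are 4 of 8, 5 of 9, "6 or more patients out of 10, 11 and 12 patients", 7 for 13 to 15 patients, and "8 or more patients out of 16, 17, 18 patients experience toxicity". A further clause stops the trial if 4 toxicities have already occurred among the first 4 to 7 patients. Nothing is printed for 19, 20, 21 or 22 patients.

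Table 2 gives early stopping probabilities of 0.006, 0.094, 0.344, 0.665 and 0.897 at true rates of 0.1 to 0.5, without a sample size. Section 4.2.4 says that monitoring against the Bayesian rules will use the department's trial conduct website.

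**The concern.** The plan gives the same stopping rule in three forms: a probability statement, a list of counts and a table of operating characteristics. They should agree. The list ends four patients before the enrolment ceiling, and the fractions and the prose seem to read 12, 15 and 18 differently. The fractions look like the first sample size at which each count applies, while the prose treats them as the last.

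The printed counts are what an ethics board or a study team can check by hand, and Table 2 is the stated protection against a toxic regimen in a surgical trial open to patients from age 1. If the counts are looser than the rule, a team working from them would continue in situations where the plan says to stop, and Table 2 would describe a stricter design than the one in use.

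**Working it through.** **Inputs (4.2.1, 4.2.3, Table 2).** Prior beta(0.6, 1.4); threshold rate 0.30; cut-off 0.8; first look at n = 8; maximum 22; the printed counts; Table 2.

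**Step 1: boundaries implied by the rule.** After x toxicities in n patients the posterior is beta(0.6 + x, 1.4 + n - x). The boundary is the smallest x with Pr(theta_E > 0.30) > 0.80.

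| n | Printed count | Count from the rule | Posterior probability at the rule's count | With one event fewer |
|---|---|---|---|---|
| 8 | 4 | 4 | 0.846 | 0.631 |
| 9 | 5 | 5 | 0.922 | 0.782 |
| 10 | 6 | 5 | 0.880 | 0.711 |
| 11 | 6 | 5 | 0.829 | 0.638 |
| 12 | 6 | 6 | 0.905 | 0.772 |
| 13 | 7 | 6 | 0.865 | 0.709 |
| 14 | 7 | 6 | 0.818 | 0.644 |
| 15 | 7 | 7 | 0.893 | 0.766 |
| 16 | 8 | 7 | 0.855 | 0.710 |
| 17 | 8 | 7 | 0.811 | 0.651 |
| 18 | 8 | 8 | 0.883 | 0.763 |
| 19 | none | 8 | 0.847 | 0.712 |
| 20 | none | 8 | 0.807 | 0.658 |
| 21 | none | 9 | 0.876 | 0.762 |
| 22 | none | 9 | 0.842 | 0.714 |

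All five printed fractions are correct, and each is the first n of its block. The prose is one toxicity too high at n = 10, 11, 13, 14, 16 and 17.

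**Step 2: stopping probabilities.** For true rate p, let f_n(k) be the probability of having k toxicities after n patients without having stopped. Then f_n(k) = (1 - p) f_{n-1}(k) + p f_{n-1}(k - 1). At each look from n = 8, the mass with k at or above the boundary is moved to stopped. This is exact, and assumes independent patients and a look after every patient. The clause for the first 4 to 7 patients does not alter the stopping probability, because 4 toxicities by patient 7 remain at least 4 at patient 8.

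**Step 3: reproduce Table 2, then vary the boundaries.**

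| Boundaries | 0.1 | 0.2 | 0.3 | 0.4 | 0.5 |
|---|---|---|---|---|---|
| Table 2 | 0.006 | 0.094 | 0.344 | 0.665 | 0.897 |
| Rule, maximum 20, last look not counted | 0.007 | 0.094 | 0.345 | 0.669 | 0.895 |
| Printed counts, nothing after 18 | 0.005 | 0.068 | 0.266 | 0.570 | 0.834 |
| Rule's counts, but ending at 18 | 0.007 | 0.092 | 0.335 | 0.652 | 0.881 |
| Printed counts plus 8, 8, 9, 9 at 19-22, look at 22 not counted | 0.005 | 0.078 | 0.317 | 0.657 | 0.897 |
| Same, look at 22 counted | 0.005 | 0.079 | 0.327 | 0.675 | 0.910 |
| Rule, maximum 22, last look not counted | 0.007 | 0.097 | 0.362 | 0.697 | 0.913 |
| Rule, maximum 22, last look counted | 0.007 | 0.098 | 0.370 | 0.710 | 0.923 |

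The second row matches Table 2 to within 0.4 points. The printed counts fall short by 0.344 - 0.266 = 7.8 points, 0.665 - 0.570 = 9.5 points and 0.897 - 0.834 = 6.3 points at 30%, 40% and 50%. At a true rate of 40% they let the trial run on with probability 1 - 0.570 = 43%, against 1 - 0.665 = 33.5% in Table 2.

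**The case against.** A reader might infer more than the documents support, in three ways.

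- **That patients 19 to 22 have no toxicity stop.** They do. The probability statement applies throughout the study, and 4.2.4 assigns monitoring to a website that works from the Bayesian rules. What is missing is a printed count. The fraction 8/18, read as the rule generates it, already covers 18 to 20, which leaves only 9 at 21 and 22 unlisted. The look at 18 also guards the entry of patient 19, and a look after patient 22 cannot prevent any enrolment.
- **That ending at 18 is what breaks Table 2.** The rule's own counts cut off at 18 stay within 1.6 points of Table 2 at every rate. Starting from the printed counts, adding 19 to 22 does recover much of the gap, so the split between the two errors depends on the order in which they are corrected. On the convention that reproduces Table 2, however, that addition still leaves 0.344 - 0.317 = 2.7 points at 30%, and six counts that contradict the rule.
- **That protection is overstated however the trial is run.** If the website applies the stated rule through 22 patients, the trial stops more often than Table 2 says at 30% to 50%. The shortfall arises only if the printed counts are used.

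These points narrow the claim but do not remove it. The prose counts are part of the plan, they contradict its rule, and nothing in 4.2.3 says which form governs.

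**Conclusion.** The point holds as a contradiction within 4.2.3, and between 4.2.3 and the 22-patient maximum in 4.2.1. The spelled-out counts are one toxicity too high at six sample sizes and are absent at four more. Used as printed, they give stopping probabilities 6.3 to 9.5 points below Table 2 at true rates of 30% to 50%.

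Table 2 describes neither the printed counts nor a 22-patient trial. It fits the probability rule at a maximum of 20 with the last look not counted. That 20 is an inference from the numerical match and from the Table 1 percentiles, which reach 20; the documents do not state it.

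The boundary errors follow directly from the stated prior and cut-off. The stopping probabilities also assume independent patients and a look after each one from the eighth. This should be corrected, because the figures are wrong as written, but the probability rule itself is intact.

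**What to change.** Reconcile the printed counts with the plan's own probability rule by regenerating them for every n from 8 to 22. As stated, the rule yields 4 at 8; 5 at 9-11; 6 at 12-14; 7 at 15-17; 8 at 18-20; and 9 at 21-22. Adding counts for 19 to 22 alone is not enough, since it would leave the six discrepant counts in place.

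Then rerun Table 2 for the 22-patient maximum, state that sample size in the table, and say whether a crossing at the look after the last patient counts as early stopping. Both sets of values are in the last two rows of the second table above. Confirm that the monitoring website is configured with the same prior, cut-off and maximum.

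The cost is a few lines in 4.2.3 and one table rerun; the prior, the cut-off and the sample size do not change.
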